5.5. Multicenter Studies

Part A is a multicenter, open-label study.

Part B is a multicenter, randomized, double-blind study. Investigative center was not a stratification factor because the large number of investigative centers would break down the intended balance within each combined stratification level by the stratified randomization method. It will not be included as a covariate in any covariate-adjusted analysis because the large number of investigative centers in this study cannot be practically incorporated into such analysis.

Part C is a multicenter, open-label study.

5.6. Adjustments for Covariates

As supportive analysis, the primary PFS and secondary efficacy endpoint OS of Part B will also be analyzed adjusting for prespecified potential prognostic factors chosen from the variables listed below, with * indicating the reference level. Detailed description as for which factors to be used will be provided for relevant analyses in later sections.

- Randomization stratification factors:
 - o EGFR mutation (exon 19 deletion or exon 21 [L858R] substitution mutation*)
 - o Gender (male or female*)
 - o Region (East Asia or other*)
 - o *EGFR* testing method (*Therascreen*[®] [Qiagen] and *Cobas*[®] [Roche] or other PCR and sequencing-based methods*)
- Other factors of interest:
 - o age (<65 years or ≥ 65 years*)
 - o age (<70 years or ≥ 70 years*)
 - o age (<75 years vs. ≥ 75 years)
 - smoking history (ever or never smoker*)

Note. The definition of "ever smoker" includes those who smoked ≥100 cigarettes, cigars, or pipe-fulls in his/her lifetime and the definition of "never smoker" is one who smoked <100 cigarettes, cigars, or pipe-fulls in his/her lifetime

- o performance status (0 or 1*)
- o initial stage at diagnosis (Stage IV or other)
- o liver metastases (yes vs no)

5.7. Study Patients

The following summaries (frequency and percentage) and listings for patient disposition will be performed:

- Patient disposition by cohort/treatment and overall: patients entered (that is, signed informed consent), entered but not enrolled (that is, screen failure), enrolled (that is, randomized, intent-to-treat (ITT) population), enrolled but not treated, treated (that is, safety population), completed, and discontinued, DLT-evaluable (Part A only), DLT-non-evaluable (Part A only)
- Reasons for discontinuation for:
 - o all treated patients as well as patients continuing on the study
 - o screen fail patients (that is, patients who entered by not enrolled)
 - o enrolled patients who did not receive any study treatment for Part A and C, or randomized patients who did not receive any study treatment for Part B
- Listings of:
 - o primary reason for all study treatment discontinuation
 - o PFS, PFS2, OS for Part B only
 - o PFS, PFS2, OS for Part C, Periods 1 and 2
 - o date of randomization for Part B only

5.7.1. Analysis Populations

The following populations will be defined for this study:

Part A Safety Population: all patients enrolled in Part A and received at least 1 dose of any study treatment. Demographics, baseline disease characteristics, dosing/exposure and AE analyses will be presented for part A safety population.

Part A DLT-Evaluable Population: patients who either completed first 2 cycles of treatment (approximately 28 days + 3 days) or discontinued from study treatment or study participation before completing first 2 cycles due to a DLT would be considered DLT-evaluable. Refer to Section 9.4.1 of the protocol for detailed DLT definitions.

Part B Intention-to-Treat (ITT) Population: This population is defined as all patients who will be randomized (enrolled) to study treatment during Part B. Patients will be grouped according to randomized treatment. This population will be used for demographics and baseline disease characteristics, study treatment disposition, efficacy, and PRO analyses.

Part B Per-Protocol (PP) population: includes all patients who are randomized and treated and do not have any major protocol deviations that could potentially affect the efficacy conclusions of the study. The PP population is a subset of the ITT population that will be defined and finalized prior to database lock for the primary PFS analysis. The PP population will be used for sensitivity analyses of OS and PFS.

Part B Safety Population: all enrolled (randomized) patients that received at least 1 dose of any study treatment in Part B. Patients will be grouped according to treatment received in Cycle 1.

The Part B safety population will be used for all dosing/exposure, AEs, and resource utilization analyses.

All the analyses for Parts A and B will be conducted separately, unless otherwise stated.

Pharmacodynamic and/or tailoring biomarker analyses will be based on the subset of ITT population in Part B from whom a valid assay result (according to laboratory guideline) has been obtained. These analyses will be included in a separate SAP or LOA.

Compliance for the PRO instruments will be reported for the ITT population. All other PRO analyses will be on the ITT population and will include those from whom a completed PRO instrument was obtained at baseline and at least one postbaseline (either during study treatment period or 30-day short-term postdiscontinuation follow-up period); thus, the actual patients included for each analysis will depend on the instrument and response variable.

A patient listing of analysis population details will be provided. This listing will be presented by treatment arm and will include: investigator site, patient identifier, inclusion/exclusion flag for each population, and reason for exclusion from each population. All patients screened will appear on this listing.

Part C ITT Population: All patients who will be enrolled to study treatment during Part C. ITT population will be used for demographic, baseline disease characteristics, and 1-year PFS rate and PFS2.

Part C Period 1 Safety Population: All enrolled patients who received at least 1 dose of any study treatment in Part C Period 1.

Part C Period 2 Safety Population: All enrolled patients who received at least 1 dose of any study treatment in Part C Period 2.

The Part C safety populations will be used for all dosing/exposure, AEs, and resource utilization analyses. The safety summaries may be provided by period.

Pharmacodynamic and/or tailoring biomarker analyses will be based on the subset ITT population in Part C from whom a valid assay result (according to laboratory guideline) has been obtained.

5.7.2. Important Protocol Deviations

The TIMP (trial issue management plan) stored in the eTMF documents the list of important protocol deviations identified for this study. These violations were selected from the major protocol deviations listed in the Study Specific Monitoring Requirements. Only the ones that could potentially affect efficacy conclusions were selected for exclusion of the per protocol population.

The list of patients (except for patients with incorrect study medication) excluded in the per protocol population will be identified prior to unblinding for the primary PFS analysis.

Non-programmable protocol deviations will be evaluated and summarized by the study Clinical Trial Manager(s). The study statistician will then combine them with the programmable ones. All programmable and non-programmable protocol deviations will be reported.

Number and percentage of patients with important protocol deviations will be reported by treatment arm and by type of deviation for Part A, B and C separately. A patient listing of important protocol deviations will also be generated.

Discrepancies between the local and central laboratory that may have an impact on treatment decisions will not be considered protocol deviations.

5.8. Demographic and Baseline Characteristics

The following patient demographic and other baseline characteristics will be summarized for each part of the study:

- Patient demographics: age (years), age group (<65 vs. ≥65 years; <70 vs. ≥70 years, <75 vs. ≥75 years; and <65, 65-74, 75-84, ≥85, gender, race, ethnicity, height (cm), weight (kg)
- Potential prognostic factors for NSCLC as listed in Section 5.6
- Baseline disease characteristics:
 - at study entry only: duration of disease (months), number of metastatic sites, tumor burden size (sum of target lesions in cm), anatomical sites of metastasis
 Note. Number of sites and anatomical sites of metastasis will be derived from radiographic assessment data collected at baseline.
 - at initial diagnosis and at study entry: disease stage, basis for pathological diagnosis (histopathological versus cytological), pathological diagnosis, histopathological diagnosis grade
- Prior cancer therapies: type of prior surgery, type of prior radiotherapy, type of prior systemic therapy
- Historical illness by MedDRA PT, presented in decreasing frequency
 Note. Patients reporting more than one condition/diagnosis within a PT will be counted only once for that PT

Comparison between the eCRF and IWRS values of the stratification factors corresponding to Part B will be performed in terms of a sensitivity analysis. Patient listings of demographic data and baseline characteristics will be provided. Patient listings of prior cancer therapies (surgery, radiotherapy, and systemic therapy) will be provided.

5.9. Concomitant Medications

A medication will be regarded as concomitant if:

• the medication was started on or after the date of first dose of study treatment and before the end of short-term follow-up;

• the medication was started prior to first dose of study treatment but was ongoing at the time of the first dose of study treatment.

The following concomitant medications used in study treatment period or the 30-day short-term postdiscontinuation follow-up period will be summarized by numbers and percentages by treatment arm, presented in decreasing frequency of the World Health Organization (WHO) drug term across treatment arms:

- All concomitant medications
- Best supportive care and select concomitant medications, including antidiarrheal agents, antiemetic agents, analgesic agents, antibiotics, antihypertensives, antifungals, antivirals, appetite stimulants, granulocyte-colony stimulating factor, erythroid growth factors, rash treatment and bisphosphonates.
 - **Note.** Such drugs to be used for programming will be identified through reviewing of the unique drug terms collected in the study.
- Premedication for ramucirumab/placebo.

The proportions of patients receiving at least one concomitant medication and the proportion reporting use of concomitant medications will be compared between the treatment arms using the Chi-square test for Part B. The concomitant medications will be summarized for Parts A and C. Patient listing of all concomitant therapies and premedications will be provided.

5.10. Treatment Compliance

The number of tablets taken relative to the number expected to be taken will be summarized for erlotinib for Part B, for gefitinib for Part C Period 1, and for osimertinib for Part C Period 2, respectively. Note that treatment compliance can only be checked for those sites where study drug was received at the site.

Ramucirumab/placebo will be intravenously administered only at the investigational sites. As a result, patient compliance is ensured.

5.11. Efficacy Analyses

There is no efficacy analysis planned for Part A. This section is applicable for Part B, unless otherwise specified.

5.11.1. Primary Efficacy Analyses

The primary efficacy analysis will be performed in the Part B ITT population. For the primary comparison of investigator-assessed PFS between the 2 assigned study treatment arms, a stratified log-rank test at alpha level of 0.04998 (2-sided) will be performed to test the following statistical hypotheses about the PFS HR for ramucirumab plus erlotinib over placebo plus erlotinib:

 H_0 : PFS $HR \ge 1.00$

H_a: PRS HR < 1.00

The stratification will be the same as that used for randomization in the IWRS. An unstratified log-rank test will also be performed.

The following analyses of PFS will also be performed:

- Summary of PFS events (number and percentage), censoring rate, and reasons for censoring
- Kaplan-Meier survival curve (Kaplan and Meier 1958) by treatment arm will be provided.
- Restricted mean difference in PFS between the treatment arms and its 95% CI, while the
 restriction time is defined by the latest time where the standard error of the PFS estimates
 are ≤ 0.075 months.
- The Kaplan-Meier method will be used to estimate parameters (medians, quartiles, and percentages), difference of percentages and associated 95% CI and p-values for landmark analyses on each treatment group at 3 month intervals, based on a normal approximation. Patients who did not have the event at the corresponding time point will be considered right-censored observations.
- HR for treatment effect will be estimated using Cox proportional hazards (PH) model (Cox 1972) stratified identically to the primary log-rank test with assigned treatment as the only covariate, reported with 2-sided 95% CIs. All randomized patients, according to the ITT principle, will be included in the analysis of this endpoint. This Cox PH model will be referred to as the primary Cox PH model henceforth.

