5.1.2. Part B

The study will enroll approximately 450 patients in 1:1 randomization (that is, approximately 225 patients will be randomly assigned to each treatment arm). The primary PFS analysis will be performed after approximately 270 PFS (approximately 40% censoring rate) events.

An interim futility analysis was conducted at 114 investigator-assessed PFS events (data cutoff date 16 October 2017), and the IDMC recommended the trial continue without modification. A nominal 1-sided alpha <0.00001 was spent in order to maintain type-I error. Assuming an HR of 0.71, this sample size yields at least 80% statistical power to detect superiority of the ramucirumab plus erlotinib arm over the placebo plus erlotinib arm, with the use of a 1-sided log-rank test and a type I error of 0.02499. If the true median PFS for the placebo plus erlotinib arm is 11 months, then the HR of 0.71 amounts to an approximate 4.5-month improvement in median PFS for the ramucirumab plus erlotinib arm under an additional assumption of exponential survival distribution.

Sample size calculation is carried out in EAST Version 6.4 (1994-2016).

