5.2. General Considerations

Part A: The analyses for Part A will be descriptive. Data analyses will be provided separately for study patients in the 2 geographic areas: 1) Japan, 2) European Union (EU) and United States, and 3) total. The list of analyses conducted for the Assessment Committee (AC) review is included in the AC charter.

Part B: All tests of treatment effects will be conducted at a two-sided alpha level of 0.05, and all CIs will be given at a two-sided 95% level, unless otherwise stated. Statistical analysis will be performed using SAS software (SAS, Version 9.2 or higher).

Part C: This part is only applicable to sites in the East-Asian region, including Japan. The analyses for Part C will be descriptive and conducted separately from Parts A and B. Results of Part C will be included in a separate addendum to the clinical study report (CSR) for Parts A and B. Safety data of Part C will be summarized by each period. Patients who do not enter Period 2 will not be included in summary safety analyses for Period 2.

This document describes the statistical analyses planned prior to final treatment assignment unblinding of the aggregate database. Any change to the data analysis methods described in the protocol will require an amendment ONLY if it changes a principal feature of the protocol. Before unblinding of the aggregate database, minor modifications or clarifications to the data analysis methods may be described and justified in this document. Any other change to the data analysis methods described in the protocol and the justification for making the change will be described in the CSR. The assumptions for each statistical method may be evaluated. If there is violation of assumptions, alternative statistical methods may be used. Additional exploratory analyses of the data will be conducted as deemed appropriate. The SAP will not be updated to reflect post-hoc analyses conducted after unblinding. These will be described in the study report as appropriate.

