5.11.2. Secondary Efficacy Analyses

5.11.2.1. Key Secondary Efficacy Analyses

For OS, the same analyses used for the analyses of the primary PFS endpoint (except sensitivity analyses based on PFS censoring rule) will be performed. One interim analysis and a final analysis for OS may be performed in this study. A hierarchical testing procedure will be employed to test OS. The OS will be tested only if PFS is significant. If PFS is not significant after the primary analysis for PFS is performed, OS will not be statistically evaluated. This comparison of OS using the same method as that for the primary analysis of PFS will be considered inferential only in case of significant results for PFS analysis (that is, a gate keeping approach was used so as not to inflate the overall type I error rate).

The OS interim analysis may be performed at the time of primary PFS analysis (approximately 270 PFS events) and the final OS analysis may be conducted later with the aim of providing as much information as possible on OS. This final analysis of OS will be performed when OS data are relatively mature (approximately 300 OS events and 35% censoring). The 1-sided type I error rate will be controlled at 2.5% by using a Haybittle Peto type spending function (p-value bound 0.0001 at the interim analysis) (Jennison and Turnbull 1999).

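### The RMST restriction time uses a standard-error limit of 0.075 'months' for an unnamed estimate; the unit does not fit the likely intent, a Kaplan-Meier probability

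*SAP*

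**What the plan says.** After the primary log-rank test, SAP Section 5.11.1 lists further PFS analyses. One is the "Restricted mean difference in PFS between the treatment arms and its 95% CI". The same bullet fixes the horizon: the "restriction time is defined by the latest time where the standard error of the PFS estimates" "are ≤ 0.075 months". It does not say whether these estimates are Kaplan-Meier probabilities, restricted means in each arm, or the difference between restricted means. It also does not say whether one arm or both must meet the limit.

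The bullet before it is the Kaplan-Meier curve. The bullet after it covers Kaplan-Meier medians, quartiles and percentages, with landmark comparisons "at 3 month intervals, based on a normal approximation".

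Section 5.11.2.1 extends the set to survival: "For OS, the same analyses used for the analyses of the primary PFS endpoint" are to be performed, except the sensitivity analyses based on the PFS censoring rule. The horizon rule therefore applies to OS as well. No other section of the SAP defines it further.

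**The concern.** The restriction time is part of what a restricted mean difference estimates: change the horizon and a different quantity is reported. A rule that sets it should be executable as written, and this one is not.

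A Kaplan-Meier PFS probability has no unit, so a standard error in months cannot belong to it. A restricted mean, or a difference between two, is in months, and the bullet is about exactly such a difference. A programmer who follows the unit reaches the restricted-mean reading. One who follows the usual logic of such rules has to discard the printed unit.

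At stake is whether the supportive comparison covers most of the PFS curve or only its first few months, and that the choice might be made after the data are seen.

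**Working it through.** **Inputs from SAP Section 5.1.2.** "approximately 225 patients will be randomly assigned to each treatment arm", so n = 225. The control median is an assumption of the plan: "If the true median PFS for the placebo plus erlotinib arm is 11 months". The hazard ratio is 0.71, survival is exponential, and the analysis follows about 270 PFS events with a one-sided type I error of 0.02499.

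**The plan's own figures reproduce.** 11/0.71 = 15.49 months, a gain of 4.49 (stated: about 4.5). 1 − 270/450 = 40% censored. Schoenfeld power at 270 events is 80.3% (stated: at least 80%). The SAP states no horizon in months to compare with.

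**Months reading, continuous event times.** The hazards are λ = ln 2/11 = 0.0630 (placebo) and 0.71 × 0.0630 = 0.0447 (ramucirumab). Without censoring before τ:

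- Restricted mean: (1 − e^(−λτ))/λ
- Var[min(T, τ)] = (1 − 2λτ·e^(−λτ) − e^(−2λτ))/λ²
- SE in one arm = √(Var/225); SE of the difference = √((Var_placebo + Var_ramucirumab)/225)

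SE = 0.075 means a variance (or, for the difference, a sum of variances) of 225 × 0.075² = 1.266. Solving for τ:

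| Estimate held to 0.075 month | τ (months) | Event-free at τ, placebo / ramucirumab | True difference at τ (months) | SE at 11 months |
|---|---|---|---|---|
| Difference | 3.49 | 80% / 86% | 0.10 | 0.344 |
| Restricted mean, placebo | 4.28 | 76% / 83% | 0.14 | 0.252 |
| Restricted mean, ramucirumab | 4.71 | 74% / 81% | 0.17 | 0.234 |

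At 11 months the standard errors are 3.1 to 4.6 times the limit (0.234/0.075 to 0.344/0.075). For comparison, the true difference at 11 months is 0.75 month. Censoring moves the horizons little: with assumed accrual of 18 to 36 months and dropout of 0 to 2% per month they stay at 3.47–3.49, 4.25–4.28 and 4.67–4.71.

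**Months reading, events dated at assessments.** Section 5.3.1 dates progression at a tumour assessment. Suppose every event is recorded at the next 6-weekly assessment. Six weeks is the interval that Section 5.2 gives for long-term follow-up before progression; using it on treatment is an assumption, and deaths are not dated separately. The three horizons become 4.24 (difference), 5.03 (placebo) and 5.44 months (ramucirumab).

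The literal range is therefore roughly 3.5 to 5.5 months. Of the planned 3-monthly landmarks, it contains only the first.

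**Probability reading.** Without censoring, the standard error of a Kaplan-Meier probability cannot exceed 0.5/√225 = 0.033, less than half the limit. Only heavy censoring late in follow-up can push it above 0.075. Simulation used uniform accrual, cutoff at the 270th event, Greenwood standard errors and the smaller arm-specific time, with 2,000 trials in each of 20 scenarios. Accrual (12 to 36 months) and dropout (0 to 15% per year) are assumptions, because the SAP gives neither.

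- Median horizon: 23.2 to 36.4 months without dropout, 26.8 to 39.2 with 15% dropout per year.
- True difference at that horizon: 2.2 to 4.0 months.
- The limit shortens the horizon in 3 to 13% of simulated trials.
- Taking the later instead of the earlier arm-specific time moves the horizon by 0.2 to 2.1 months and the true difference by 0.03 to 0.18 month.

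These simulations use continuous event times and leave out censoring rules 7 and 8 of Table JVCY.5.1, so they show scale only.

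**The case against.** The strongest reply is that this is a stray unit and nobody would be misled. A latest time at which a standard error stays within a limit suggests estimates indexed by time, which is what a Kaplan-Meier curve supplies. The neighbouring bullets are both Kaplan-Meier analyses. And 0.075 is a natural size for the standard error of a probability but makes little sense as a limit for a restricted mean in months. On that reading the limit seldom binds and the one-arm-or-both question hardly matters.

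Most of this stands. The probability reading is the likelier one, and a reader who infers that the restricted mean comparison will in fact stop at 3.5 to 5.5 months goes further than the SAP supports: it nowhere says that restricted means were intended. The literal horizons also depend on how events are dated and should be quoted only as a rough range.

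What does not stand is that nothing needs correcting. The unit sits in the threshold of an operative rule, no other section overrides it, and the likely intent is an inference. Medians and quartiles are also in months, but they are not indexed by time and so do not rescue the wording.

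A reader might also infer that the primary PFS conclusion is exposed. It is not: the restricted mean difference is listed among additional analyses and has no alpha and no decision rule.

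**Conclusion.** The concern holds as a minor error. The rule does not name the estimate, and its unit is wrong for the likely intent. The two readings give horizons of roughly 3.5 to 5.5 months and about 23 to 39 months, with true differences of about 0.1 to 0.2 month (continuous event times) and 2.2 to 4.0 months.

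The short horizon rests on the Section 5.1.2 design and on the dating of events; that it lies well below 11 months holds either way. The long horizon rests on assumed accrual and dropout, but it was practically the end of follow-up in every scenario tried. The same ambiguity passes to OS; its size cannot be given, because the SAP states no OS median. Leaving open whether both arms must meet the limit is a small point, worth at most about 0.2 month in the true difference.

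The primary log-rank test, hazard ratio, power, medians and landmark analyses are unaffected.

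**What to change.** Before aggregate unblinding, delete 'months' and state the rule as: *the latest time at which the standard error of the Kaplan-Meier PFS probability (OS probability for OS) is ≤0.075 in both treatment arms*, that is, the smaller of the two arm-specific times.

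If restricted means in months were really meant, say so, state whether the limit applies to each arm or to the difference, and reconsider 0.075, which would end the comparison at about half the assumed control median or earlier.

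The cost is one sentence. SAP Section 5.2 already provides for it: before unblinding of the aggregate database, "minor modifications or clarifications to the data analysis methods may be described and justified in this document".
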